### 7.2.3 Entry into Study Treatment Phase

If a subject has met all the inclusion and exclusion criteria described in Section 5.3, and has a herpes labialis lesion in Stage 1 or Stage 2, the subject will then be allowed into the Treatment Phase of the study and instructed to open the Treatment kit containing the study material and begin treatment. The subject will be asked to schedule their Visit Day 1 clinic visit for later that day, if possible; otherwise the visit must be scheduled as early as possible the following day anytime within 24 hours of the time at which a subject calls and is allowed to enter the Treatment Phase of the study.

A subject who does not meet one or more of the Inclusion Criteria (Section 5.3.1), or certain Exclusion Criteria (specifically Treatment Phase Exclusion Criterion #1 - #5; Section 5.3.2) may still be eligible for continuing in the study. Those subjects will be instructed that they cannot be entered into the Treatment Phase of the study at that time, but must wait until their next outbreak at which time they can call in again to see if they qualify to begin the study treatment. The list of those criteria where subjects who do not meet those criteria can still participate in the study, but must defer their entrance into the Treatment Phase until their next cold sore recurrence, is provided below:

- The subject reports a lesion stage later than Stage 2 (Treatment Phase Inclusion Criterion #1).
- A female subject is not using a medically acceptable form of birth control (Treatment Phase Inclusion Criterion #2). In this instance, the subject will be instructed to return to the clinic for another pregnancy test. Once that test is shown to be negative, the subject will be told to resume proper contraception and can then call in again at the next lesion outbreak.
- The subject does not have immediate access to the clinical trial material kit (Treatment Phase Inclusion Criterion #3). In this case they will be asked to call again when he or she has the kit at hand. At the time of their second phone call they also will be asked again about the stage of their lesion to be certain that the lesion has not progressed beyond Stage 2.
- The subject cannot appear for a clinic visit within 24 hours from the time of enrollment into the Treatment Phase of the study (the time of the subject's call to establish entry into the Treatment Phase of the study), or is unable to return to the clinic daily for the full 14 day duration of the study if necessary (Treatment Phase Inclusion Criterion #4).
- The subject has any evidence of active malignancy or immunodeficiency disease within the last 30 days (Treatment Phase Exclusion Criterion #1). As also noted in

Exclusion Criterion #1, subjects who have completed therapy and are considered unlikely to relapse or who have had surgery and do not have any evidence of disease, are eligible for the study and therefore could begin the study treatment provided they meet all other inclusion and exclusion criteria.

- A subject has used topical steroids on or near the face or systemic (oral, intravenous) steroids within the last 30 days (Treatment Phase Exclusion Criterion #2). As also noted in Exclusion Criterion #2, use of inhaled steroids does not exclude a subject from the study; such subjects, providing they meet all other criteria, can be entered into the Treatment Phase of the protocol.
- A subject has used an NSAID within the last 12 hours of calling the clinic to report the lesion (Treatment Phase Exclusion Criterion #3).
- A subject has used an investigational drug and/or device within the last 30 days (Treatment Phase Exclusion Criterion #4).
- A subject has used any anti-viral drug, or any other medication, including home remedies, intended to treat cold sores (e.g. lysine, tea tree oil, honey) within the last 30 days, or used any topical medication to treat the current active herpes simplex labialis lesion (Treatment Phase Exclusion Criterion #5).

Except for those Treatment Phase Exclusion Criteria noted above, specifically #1 - #5, a subject meeting any of the other exclusion criteria will no longer be able to participate in the study and he or she will be asked to report to the clinic in order to return their sealed kit.

#### **7.2.4 Drug Administration**

Each subject, upon entering the Treatment Phase of the study, will be instructed to treat their lesion immediately using the solution and single-use applicators in the Treatment kit. The subjects, according to the randomization scheme, will begin self-administration of the applications of either Merlin or placebo solution. Treatment Day is the first day of treatment for all subjects.

At the time of the subject's call to enter the Treatment Phase of the study, the clinic should review the method and schedule of treatment applications with the subject.

For the first and all subsequent treatments, each subject will administer three (3) applications of Merlin or placebo, depending upon how a subject has been randomized, performed within a time period of 40 minutes or less, while allowing time for the solution to dry on the lesion between applications. A total of twelve (12) Merlin or placebo treatments, i.e. thirty-six (36) applications, will be administered over the ensuing 96 hours (4 days) from the time of the first treatment. On each day, treatments will be administered six (6) hours apart ( $\pm$  1 hour), with a maximum of three treatments each day. The first treatment will be administered on Treatment Day (Day 0), and then repeated at 6 ( $\pm$  1 hour) and 12 hours ( $\pm$  1 hour) after the first treatment, time permitting.

Subjects who, upon self-examination outside of the clinic, or upon evaluation in the clinic, are found to have herpetic lesions that have reached the ulcer/soft crust stage (Stage 4) should be instructed to discontinue all remaining treatments. If the observation of the lesion reaching Stage 4 is made by the subject outside of the clinic, the subject should call into the clinic as soon as possible after making this observation to confirm the accuracy of their assessment and to report the event.

Subjects who are unable to begin treatment for any reason, aside from those listed in Section 7.2.3, are to be discontinued from the study; those subjects are to return to the clinic to turn in their clinical trial materials and are not to be followed for safety or efficacy. Subjects, though, who are able to complete any part their treatment, even only a single application of the solution to the face, are to continue to participate in the study as planned, including appearing for all safety and lesion assessment clinic visits.

## 7.2.5 Subject Diaries

Each subject will be instructed to record into their diaries the date and time of their first treatment, the stage of their lesion, and his or her assessments of pain as described in this section. The recording of the assessments of lesion stage and pain level are to be done three times per day, just prior to initiation of each treatment (i.e. just prior to the first application in a set of three (3) applications). After the course of treatment is completed, assessment of lesion stage and pain level will continue 3 times daily with approximately 6 hours in between each assessment until the lesion is healed. The subject will also be instructed to bring the diary to each office visit so that the Investigator or trained designee can review it.

### 7.2.5.1 Pain Assessment

At the time of the subject's call to enter the Treatment Phase of the study, the clinic will ask the subject to provide the time of the onset of any pain caused by the herpes lesion to be treated along with the severity of any lesion pain.

The severity of lesion pain will be based on the following rating scale:

1 = None	No pain
2 = Mild	Pain is present in such a way that the subject is only vaguely aware of it and it does not interfere with daily activities
3 = Moderate	The subject is aware of pain at all times, but it does not interfere with daily activities
4 = Severe	Level of discomfort of pain is such that it interferes with daily activities.

As noted in Section 7.2.5, the subject will also record in the diary, just prior to each treatment, the severity of any lesion pain. After the course of treatment is completed, assessment of pain level will continue 3 times daily with approximately 6 hours in between each assessment until the lesion is healed.

### **7.3 Follow-up Visits (Visit Days 1-14)**

Each subject entered into the Treatment Phase of the study is to come in for an office visit every day, (preferably about the same time of day each day, if possible), following treatment until the clinician or trained designee determines that the treated lesion has reached Stage 7, up until at least Visit Day 3 and at most until Visit Day 14. As subjects might call any time of the week, and the Treatment Phase of the study could last as many as 14 days, clinics must be staffed with personnel, trained in lesion assessment, 7 days a week. Every effort should be made to get the subject to come to all their study visits. If a subject misses a visit, the study clinic visits still end for them on Visit Day 3 if their lesion has reached Stage 7 by then, or on the day their lesion reaches Stage 7, or Visit Day 14, whichever comes first.

#### **7.3.1 Clinical Lesion Assessment**

When possible, clinical lesion assessment of a subject should be performed by the same evaluator on each day. If the same lesion evaluator cannot perform all the lesion assessments for a given subject, the person taking over the lesion assessment of that subject should observe the lesion with the previous assessor to ensure they are in agreement with the stage. (The name(s) of any clinical staff member(s) involved in the evaluation of a given subject's lesion stage for that day should be noted in the subject's source documents.) The Investigator, or trained designee, acting as the lesion evaluator, will mark, on the first clinic visit, the location of the treated lesion on a facial diagram included in the subject's source records and will score the lesion on each subject at each visit. A trained designee should be a member of the clinical personnel who is a dermatologist/ physician or someone with a clinical background with the ability to evaluate the stages of a herpetic lesion.

The herpes lesion treated by the subject will be considered part of the primary recurrence for evaluation. Any other herpes lesions that appear within 10 mm of that first lesion, on the same calendar day, will also be considered part of the primary lesion complex. All other lesions located at least 10 mm from the first lesion, or occurring within 10 mm of the first lesion on any other day after the day of the first lesion outbreak, will be defined as secondary lesions. Only lesions within the primary lesion complex will be scored for lesion staging for efficacy analysis. Secondary lesions will not be scored for lesion staging. If the Investigator determines that secondary lesions are typical for a given subject, then the observation of such secondary lesions in that subject need not be captured in the CRF. If, however, the Investigator concludes that secondary lesions are not usual for a given subject, then the observance of a secondary lesion in that subject may be captured and followed as an Adverse Event.

The lesion scores are defined as follows:

0. Prodrome
1. Erythema
2. Papula/edema
3. Vesicle/pustule
4. Ulcer/soft crust
5. Hard crust
6. Residual swelling/dry flaking
7. Normal skin

Classical lesions are those lesions that pass through Stages 3, 4 **or** 5 at any lesion assessment. Non-classical (aborted) lesions are lesions that never pass through Stages 3, 4, **or** 5 prior to healing at Stage 7.

A herpetic lesion typically progresses to higher level stages and therefore would not be expected to proceed from a higher number stage to a lower number stage. The exception to this would be the case where a subject has a Stage 5, hard crust, lesion in which the scab is inadvertently knocked off, e.g. while washing. In that instance, the lesion would “go backwards” from a Stage 5 lesion to a Stage 4. This expected progression of the herpetic lesion should be kept in mind as a guideline in the evaluation of the lesion stage. Any time, therefore, a lesion is observed to “go backwards,” a note should be made in the CRF as to why, if the reason can be determined, the lesion reversed its progression.

The study clinic visits end for a subject when (1) the treated lesion is no longer present (Lesion Stage 7 for both classical and non-classical lesions) and there have been clinic assessments every day up until at least Visit Day 3, or (2) at Visit Day 14, whichever occurs earlier.

### 7.3.2 Diary Review

At each clinic visit, the investigator, or trained designee, will assess the subject's cold sore lesion before reviewing entries in the diary. In reviewing the diary, the investigator, or trained designee, will review the subject assessments for consistency and completeness. Should any apparent errors or incomplete entries be found in the diary, the subject will be informed of these issues, and instructed as to how to properly complete the diary in the future; no retroactive changes, though, are to be made in the diary. Any blanks that should have been completed prior to the clinic visit should be marked by the diary reviewer, so as to prevent later completion, and initialed and dated by the reviewer.

### **7.3.3 Lesion Size Assessment**

At each clinic visit, the Investigator, or trained designee, will use a disposable ruler, supplied by the sponsor, to measure the lesion size. Two measurements will be taken: 1) the length of the longest dimension of the lesion; 2) the maximum length of the lesion dimension perpendicular to the axis of the first measurement taken.

### **7.3.4 Pain Assessment**

At each clinic visit, the Investigator, or trained designee, will review the subject entries in the diary. In reviewing the diary, the Investigator, or trained designee, will inspect the subject entries for timing of dosing and pain assessments with regard to consistency and completeness. Should any apparent errors or incomplete entries be found in the diary, the subject will be informed of these issues, and instructed as to how to properly complete the diary in the future; no retroactive changes, though, are to be made in the diary. Any blanks that should have been completed prior to the clinic visit should be marked by the diary reviewer, so as to prevent later completion, and initialed and dated by the reviewer.

### **7.3.5 Safety Assessments**

The subjects will be questioned concerning their well-being at the time of each clinic visit. Questions will be posed in a non-specific manner so as not to bias the response. The subjects will also be instructed to inform the study physician and/or nurses of any adverse events that may occur at any time during the study. On Visit Day 1 the subject should be asked about any adverse events occurring since treatment on Treatment Day, so as to capture any adverse events that took place since their treatment. Subjects who discontinue prior to Visit Day 3 but have administered any treatment must be followed for safety, by telephone or clinic visits, as deemed appropriate by the Investigator, until at least Visit Day 3.

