## 5.4 Restrictions During the Treatment Phase

- 5.4.1 The subject is not to use any oral or topical prescription or over-the-counter medications to treat the current herpes labialis lesion, or apply any cosmetics, lip balms, ointments, moisturizers or home remedies to the affected area.
- 5.4.2 The subject is not to use any pain medication or non-steroidal anti-inflammatory agent (NSAID), except low doses of aspirin ( $\leq 325$  mg/day) used for cardiovascular purposes, during the Treatment Phase of the study.
- 5.4.3 The subject is not to mechanically disrupt the lesion (i.e. scrubbing, lancing, shaving the area, rubbing with alcohol, etc.).
- 5.4.4 Merlin contains an alpha hydroxyl acid that may increase the skin's sensitivity to the sun and particularly the possibility of sunburn. Subjects should therefore limit sun exposure while using Merlin, and for one week afterwards.

A subject who does not meet one or more of the Inclusion Criteria or certain Exclusion Criteria may still be eligible for continuing in the study. Those subjects would be instructed that they cannot be entered into the Treatment Phase of the study at that time, but must wait until their next outbreak at which time they can call in again to see if they qualify to begin the study treatment. See Section 7.2.3 for further details.

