 To be performed by subject. Merlin administrations will begin on Treatment Day. Most typically, it is expected that subjects will treat outside of the clinic on Treatment Day, and come in within 24 hours, (on Visit Day 1), for their first lesion evaluation. If, however, a subject can come in to the clinic for a lesion evaluation the same day as their treatment starts, then Treatment Day and Visit Day 1 will coincide. Treatments will continue through at least Visit Days 1, 2, and 3. If Treatment Day and Visit Day 1 are separate days, then treatment on Visit Day 4 will be administered only if the subject was unable to complete all three (3) sets of treatments on Treatment Day. If Treatment Day and Visit Day 1 coincide, then treatment on Visit Day 5 will be administered only if the subject was unable to complete all three (3) sets of treatments on Treatment Day (Visit Day 1). In either instance a total of twelve (12) treatments (36 applications) over 96 hours from the time of the first treatment is the maximum duration of treatments.

 The first lesion scores, up until first visible signs of a herpetic lesion, are determined by the subject prior to the first treatment. All other lesion scores are determined in the clinic by the Investigator or the Investigator's trained designee.

 For women with child-bearing potential. On Treatment Day "Pregnancy Status" will be determined by asking the subject if she is pregnant or if she has changed her contraceptive practice such that there might be a significantly increased likelihood that she could have become pregnant.

 Treatment Day is the first day a subject reports visible signs of a herpetic lesion, as confirmed by telephone, and is instructed to begin treatment. If the subject can visit the clinic that same day, Treatment Day will coincide with Visit Day 1.

 Minimum duration of study for all subjects, i.e., three (3) consecutive days of clinic visits for lesion, adverse event and concomitant medication assessment.

 Treatment Day Adverse Events will be reported to clinic at the first clinic visit on Visit Day 1.

 Subjects who discontinue prior to Visit Day 3 but have administered any treatment should be followed for safety until at least Visit Day 3.

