### **7.4 Follow-Up Telephone Assessment**

Two weeks, or up to 3 weeks, if there are scheduling issues, after the subject has completed the Treatment Phase of the study (complete healing of the herpetic episode or Visit Day 14, whichever is earlier) the clinic will contact the subject by phone for a final safety evaluation. Any new adverse events that have occurred since the subject's last clinic visit should be collected at this time.

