Once the SAE form is complete, the Medical Monitor will forward it, by email, to the Vice President of Clinical Research at Topical Remedy (email: [contact]; [contact]) for review. The Vice President of Clinical Research will send any comments to Drug Safety. Drug Safety will track the SAE information and forward a desk copy of the complete SAE report to Topical Remedy, LLC.

Adverse events, whether serious or non-serious, will be followed to resolution or until the condition stabilizes, is otherwise explained, or the subject is lost to follow-up, up to a maximum of 30 days following the subject's last clinic visit. Adverse events, whether serious or non-serious, will be captured up to 2 weeks following the last clinic visit, and followed up to a maximum of 30 days following the subject's last clinic visit. Where appropriate, medical tests and examinations will be performed to document resolution of event(s). Outcome may be classified as resolved, improved, unchanged, worse, fatal, or unknown (lost to follow-up). Following the resolution of any study associated adverse events or after the completion of the Treatment Phase of the study, there will be no further adverse event reports for that subject.

While pregnancy itself is not considered to be an AE, any pregnancy complication or elective termination of a pregnancy for medical reasons will be recorded as an AE or SAE (as appropriate). A spontaneous abortion is always considered to be a SAE.

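### The 2-week safety call is not assigned to treated subjects who withdraw before healing or Visit Day 14, so no scheduled contact looks for their new or delayed adverse events

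*Protocol*

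**What the plan says.** Five parts of the protocol bear on safety follow-up after a treated subject leaves.

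- **Minimum contact.** Section 7.3.5 says "Subjects who discontinue prior to Visit Day 3 but have administered any treatment must be followed for safety", and sets the manner and length as "by telephone or clinic visits, as deemed appropriate by the Investigator, until at least Visit Day 3". Table 7-1 footnote 10, repeated in SAP Section 5, has the same minimum but weakens the verb: such subjects "should be followed for safety until at least Visit Day 3". Both rules cover only discontinuation before Visit Day 3.
- **The safety call.** Section 7.4 places a call that collects new adverse events 2 weeks (up to 3) "after the subject has completed the Treatment Phase of the study (complete healing of the herpetic episode or Visit Day 14, whichever is earlier". Footnote 11 uses the same trigger. Neither mentions discontinuation.
- **Capture window.** Section 8 says adverse events "will be captured up to 2 weeks following the last clinic visit, and followed up to a maximum of 30 days following the subject's last" visit to the clinic. A later sentence in the same section closes reporting for a subject once study-associated events have resolved or the Treatment Phase is over.
- **Withdrawal.** Section 9 asks for the necessary safety assessments where possible, and follows subjects who have an adverse event for up to 30 days after the last study visit.
- **Sun precaution.** Section 5.4.4 says "Subjects should therefore limit sun exposure while using Merlin, and for one week afterwards".

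**The concern.** Read together, these sections leave a treated subject who withdraws from the study without a scheduled contact designed to find new adverse events. Before Visit Day 3 the explicit duty is a minimum of two or three days from first treatment. From Visit Day 3 to Visit Day 13, no contact after withdrawal is scheduled at all. The one contact meant to pick up late events is tied to an endpoint that these subjects do not reach.

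Adverse events are the only safety endpoint (Protocol 10.2.2, SAP 6.2). Every subject who entered the Treatment Phase and applied any solution is in the Safety Population (Protocol 10.3.1, SAP 7.1.1). The tables give the number and percentage of subjects with events (Protocol 10.6, SAP 7.12) and make no allowance for how long each was observed. If one arm lost more subjects than the other, its events would be looked for less completely, and the percentages would not be comparable.

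**Working it through.** The plan states no figure for this point, so there is nothing to reproduce. The check is a reading of the triggers, followed by calendar arithmetic.

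**Who is assigned the call?** Section 7.4 fires at healing or Visit Day 14, whichever comes first. A subject who withdraws unhealed before Visit Day 14 meets neither condition. The protocol can name discontinuation when it means to: 7.3.5.1 sets its 2-week pregnancy-reporting period from completion of the Treatment Phase or from discontinuation. Section 7.4 has no such alternative.

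**Does Section 8 fill the gap?** Its 2-week window is not limited to completers, but three things stop it from working for withdrawals:
1. No contact is scheduled within it for them.
2. It starts at the last clinic visit, so it has no start for someone who treated at home and never attended.
3. The closing sentence of Section 8 can be read as ending reporting once an event has resolved. It also conflicts with the 7.4 call for completers.

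**Timing for withdrawal before Visit Day 3.** Let day 0 be Treatment Day. Table 7-1 footnotes 4 and 7 allow Visit Day 1 to be a separate day or the same day.

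- End of sun-avoidance period = day of last application + 7 (5.4.4).
- Shortfall = that end minus the day of Visit Day 3.
- End of Section 8 window = day of last clinic visit + 14.

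| Visit Day 1 | Visit Day 3 | Last application | Sun period ends | Shortfall |
|---|---|---|---|---|
| Separate (day 1) | day 3 | day 0 | day 7 | 7 − 3 = 4 |
| Separate | day 3 | day 1 | day 8 | 8 − 3 = 5 |
| Separate | day 3 | day 2 | day 9 | 9 − 3 = 6 |
| Same (day 0) | day 2 | day 0 | day 7 | 7 − 2 = 5 |
| Same | day 2 | day 1 | day 8 | 8 − 2 = 6 |

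The required contact alone therefore stops 4 to 6 days before the sun-avoidance period does.

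If the Section 8 window were carried out, it would run to day 15 or 16 (last visit day 1 or 2), or to day 14 or 15 (last visit day 0 or 1). That is 6 to 9 days beyond the sun period. The window is long enough; the missing piece is a contact.

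**Comparison with completers.** A subject healed by Visit Day 3 (day 2 or 3) is called between day 2 + 14 = 16 and day 3 + 21 = 24. A subject seen to Visit Day 14 (day 13 or 14) is called between day 13 + 14 = 27 and day 14 + 21 = 35.

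**How many subjects?** The documents give no withdrawal rate. Taking 5% to 15% purely as an assumption, 0.05 × 150 = 7.5 and 0.15 × 150 = 22.5, so about 8 to 23 of the 150 treated subjects would not be assigned the call.

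**The case against.** The strongest reply is that the protocol already protects most of the subjects one would worry about, and much of this stands.

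- Section 7.2.4 keeps anyone who made even one application in the study for all safety and lesion visits. A subject who stops applying solution because it burns, but stays in the study, is seen to healing or Visit Day 14 and then called.
- Sections 8 and 9 follow a known adverse event for up to 30 days after the last visit, so a withdrawal caused by a reaction is followed for that reaction.
- Visit Day 3 is a minimum, and Section 7.3.5 also tells subjects to report events at any time during the study.
- The week in 5.4.4 is an instruction to limit sun exposure. It does not say that sensitivity lasts a week, and it is not an observation period.
- Safety is summarised descriptively without testing (SAP 7.1.1 and 7.2), so no formal inference is affected.

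A reader might therefore say that 7.4 is merely silent about withdrawals and that a sensible site would call them anyway. That part does not stand. The trigger is defined in 7.4 itself, 7.3.5.1 shows discontinuation named where it is intended, and a site following the text would not make the call. Following a known event is also different from asking about new ones.

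**Conclusion.** The gap is real but narrow: new or delayed adverse events in treated subjects who withdraw from the study before healing or Visit Day 14. For withdrawals before Visit Day 3, the contact actually required ends 4 to 6 days before the sun-avoidance week. For withdrawals from Visit Day 3 to 13, no contact after withdrawal is scheduled.

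A reader might infer more: that follow-up ends at Visit Day 3 for the subjects most likely to have reacted, or that every withdrawal receives only a small fraction of a completer's follow-up. The documents support neither. Visit Day 3 is a minimum, known events are followed, and no reasons for discontinuation are given. A withdrawal at Visit Day 10 has already had nine or ten days of scheduled daily visits. Treatment ends within 96 hours, so the sun period is over by about day 4 + 7 = 11, and withdrawals after that are past it.

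Uneven ascertainment between arms is conditional on unequal withdrawal, which the documents neither predict nor quantify. This is an inexpensive improvement to the only safety endpoint and does not undermine the efficacy conclusions.

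**What to change.** In Protocol 7.4 and Table 7-1 footnote 11, apply the existing 2-week (up to 3-week) safety call to every subject who applied any study solution, timed from the earlier of Treatment Phase completion or discontinuation. If the last application is no later than discontinuation, a call at 14 days falls at least 14 − 7 = 7 days after the sun-avoidance period, so no separate rule is needed for that period.

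Then reconcile the surrounding text with the call:
- In 7.3.5 and footnote 10, keep Visit Day 3 as an interim minimum, point to the call as the last collection of new events, and use the same verb in both places.
- In Section 8, give the 2-week window a start for subjects with no clinic visit, and reword the sentence that closes reporting so that it does not precede the call.
- Carry footnotes 10 and 11 across to SAP Section 5.

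The cost is wording plus one telephone call per early withdrawal, using a procedure that sites already have. Some withdrawn subjects will decline or not answer, so the disposition summary should report by arm how many were reached.
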